6.4.3. End of Study visit (Up to 6 weeks after surgery)

End of study visits to be scheduled during the hospitalized post-operative recovering period, up to 6 weeks after surgery.

- Physical exam (review of the major body systems, vital signs (weight, heart rate, blood pressure and tympanic body temperature)
- ECOG Performance status
- Blood samples for routine haematology and serum biochemistry ([Table 9-1](#)) or will be recorded if already available in the patient medical record.
- Adverse events and concomitant medications deemed to be related to TG02-treatment

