TG02 has been administered to 4 humans. The RAS oncogene peptides have no intrinsic activity per se, but in combination with GM-CFS immune activity can be elicited. The Safety Steering Committee evaluated the safety data after 3 patients had each completed 4 weeks of treatment. There were no safety issues in these patients. Furthermore, no SAE related to trial medication has been reported for any patients including the 4th patient who has completed the trial. In addition, significant clinical data exists for its precursor vaccine, TG01, which contains 7 of the 8 mutant RAS peptides present in TG02. TG01 in combination with GM-CSF has been shown to be immunogenic, with acceptable tolerability. TG01 has been investigated in an early Phase II clinical trial, with evaluation of its efficacy in the adjuvant setting for pancreatic cancer patients in combination with gemcitabine. In the modified cohort of this trial, where the induction course of TG01 is similar to that used in the TG02 study, only expected adverse events have been related to the treatment and all of these have been mild in severity (see Investigators Brochure) with the exception of one Grade 3 event of fatigue. No SAEs related to TG01 or GM-CSF were reported. The trial has completed recruitment. Final report is expected Q4 2018.

As TG01 has been shown to be immunogenic with acceptable tolerability with the exception of hypersensitivity reactions which appear to be associated with the use of

gemcitabine as events occurred only after several cycles of chemotherapy or in the period immediately after the end of gemcitabine treatment (Palmer 2015). It is anticipated that TG02 will have a similar good safety profile in the absence of chemotherapy.

TG02 has no intrinsic activity per se and is administered in combination with the immunomodulator GM-CSF. This GM-CSF/TG02 combination is referred to as TG02-treatment in this study protocol.

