6.4.4. Study Flow Chart

The schedule of visits is presented in [Table 6-1](#). After screening a minimum of eight and maximum 14 weeks between initiation of TG02-treatment and resection surgery is anticipated with a follow up period of 4 weeks after surgery.

Table 6-1: Schedule of visits

Week	Screening within 2 weeks	Treatment period (Pre-surgery) (weeks 1-6)					Wk 8±4 days Surgery	If Surgery Wk 8-10	If surgery is Wk 10	If Surgery Wk 10-14	End of study visit ^o Up to 6 wk after surgery
		1	2	3	4	6					
Day		1	8	15	22	36	50	51-63	64	65-92	See footnote ^o
Informed Consent	X										
Patient eligibility	X										
Pregnancy Test	X										
Medical History	X										
Physical Examination ^h	X	X		X		X	X		X		X
Vital Signs ^h	X	X	X	X	X	X	X		X		X
12-lead ECG	X										
ECOG ^h	X	X	X	X	X	X	X		X		X
DTH (TG02) test ^{j,q}		X			X	X	X ^b		(X ⁱ)		
Immunology Sample ^h (PBMC)		X					X ^e			X ^g	
TG02-treatment ^p (TG02/GM-CSF)		X	X	X	X	X			(X ^f)		
Pembrolizumab ^k					X	X	X ^s		X ^t		
Haematology ^h	X	X		X		X	X		X		X ⁿ
Biochemistry ^h	X	X		X		X	X		X		X ⁿ
CEA (biomarker)	X						X ^l		X ^g	X ^g	
CTC (Circulating Tumour Cells)		X					X ^l			X ^g	
CT chest/abdomen/ Pelvic	X										
MRI (if standard Hospital procedure (re-staging))	X	As indicated									
FDG PET/CT	X ^r						X ^g	X ^g	X ^g	X ^g	
Tumour Biopsy	X ^c										
Surgery and resection of tumour tissue ^m							X ^d	X ^d	X ^d	X ^d	
Adverse Events		Continuously									X ^a
Concomitant medications	X	Continuously									X ^a

- a: Deemed to be related to TG02-treatment
- b: If surgery is scheduled to be done in week 8, DTH (TG02) injection to be done approximately 48 hours prior to surgery.
- c: For patients receiving chemo-radiation before enrolment into study, core biopsy of target colorectal tumour should be taken after chemo-radiation and during the screening window (2 week) and as close as possible to the first TG02-treatment (day 1, week 1). For patients not having chemo-radiation before enrolment into the study, a core biopsy of target colorectal tumour can be taken within the last 4 weeks but as close as possible to the first TG02-treatment (day 1, week 1). If a pre TG02-treatment biopsy has been taken for diagnostic workup as hospital procedure, this biopsy, if adequate for the study specific immune analysis and no intervening treatment has been given, can also be used.

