- d: Tumour tissue taken during resection. If for any reason, the patient will not have surgery a biopsy will be obtained if possible.
- e: To be done 2-0 days before surgery
- f: If surgery is scheduled for week 10, there will be no TG02-treatment given at week 10. If no surgery at week 10, the last TG02-treatment to be given at week 10.
- g: As close as possible up to the date of surgery.
- h: At the visits when TG02 and/or TG02-treatment (and pembrolizumab in Part II) is scheduled, the assessments should be performed prior to the treatments.
- i: Only to be taken for patients who have surgery after week 10 and had a negative DTH outcome at week 8. DTH (TG02) injection to be done 48 hours prior to surgery.
- j: Assessment of DTH (TG02) injection site to be done 48 hours (+/- 4 hours) after each DTH (TG02) injections by the patient in a study specific diary.
- k: Only applicable in Part II of the protocol
- l: To be done prior to surgery
- m: Allowed time for surgery (resection specimen) scheduled for week 8 is + 2 week and allowed time for surgery (resection specimen) scheduled for week 10 is + 4 week
- n: Blood samples for routine haematology and serum biochemistry to be recorded if already available in the patient medical record (standard of care)
- o: End of study visits to be scheduled during the hospitalized post-operative recovering period, up to 6 weeks after surgery.
- p: TG02-treatment is a combination of the two IMPs: GM-CSF and TG02. When TG02-treatment is administered, GM-CSF is to be given as an intradermal injection 15-30 minutes before the TG02 intradermal injection. GM-CSF and TG02 are administered as 2 separate intradermal injections, 15 to 30 minutes apart, at the same site in the upper arm. After any TG02-treatment the patients will be monitored for heart rate and blood pressure at 5, 10 and 30 minutes and then every 30 minutes thereafter for up to 2 hours post administration
- q: In addition, TG02 will, at certain time points, be administered intradermally (without prior administration of GM-CSF) in the lower area of the contra lateral arm as DTH test. The administration of GM-CSF (0.10 mL reconstituted GM-CSF) and TG02 (0.10 mL reconstituted TG02) has to be strictly intradermal.
- r: Should be within the last 4 weeks prior to first TG02-treatment.
- s: If surgery is scheduled after Day 50/Week 8, pembrolizumab will be given at Day 50/Week 8.

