8. TRIAL TREATMENT(S) AND REGIMEN OF INVESTIGATIONAL MEDICINAL PRODUCTS

8.1. Identity of Investigational Medicinal Product(s) (IMPs)

The TG02-treatment (GM-CSF/TG02) is manufactured according to Good Manufacturing Practice (GMP) standard.

In Part I the IMPs consists of two different products in two separate vials, 1 vial containing TG02 and 1 vial containing GM-CSF. In Part II, in addition to TG02 and GM-CSF, a third IMP, pembrolizumab will be used.

TG02

TG02 is a sterile dry white solid powder consisting of the eight drug substance peptides in equal amounts (weight net peptide) (Baccinex SA, Courroux, Switzerland/Bachem Distribution Services, GmbH).

TG02 is produced by lyophilisation of a sterile aqueous solution of the drug substance peptides. No additional ingredients are present in the TG02 drug product. Each vial of TG02 contains 2.4 mg of the drug substance peptides.

TG02 is supplied as a single dose in 2 mL clear glass vials. All the primary packaging materials used are in conformance with the European Pharmacopoeia (EP) and US Pharmacopoeia (USP).

TG02 drug product is to be reconstituted in water for injection (WFI) before administration to the patient. Patient will receive TG02 at a dose of 0.80 mg/injection.

An accountability log will be kept to track the use of TG02.

GM-CSF (Immunomodulator)

GM-CSF in the form of lyophilised recombinant human GM-CSF expressed in E-coli (Amoytop Biotech Co, Ltd, Xiamen, China) is used as immunomodulatory.

GM-CSF is a sterile dry white solid powder consisting of human recombinant GM-CSF and the excipients mannitol, macrogol 4000, human albumin, dibasic sodium phosphate and monobasic potassium phosphate. Each vial of GM-CSF contains 100 µg (1.0x10⁶ IU) Molgramostim. GM-CSF is supplied in a 2 mL clear glass vial.

GM-CSF is to be reconstituted in water for injection (WFI) before administration to the patient.

An accountability log will be kept to track the use of GM-CSF.

Pembrolizumab (Only Part II):

A fixed dose of 200 mg pembrolizumab will be administered as an intravenous infusion. The product will be provided as a 50 mg lyophilized powder in a single-use vial for reconstitution in sterile water for injection, or as a vial of 4 mL of concentrate containing 100 mg. Pembrolizumab should be administered according to the latest version of the

Summary of Product Characteristics (SmPC), and dosed according to available guidelines for the use of this drug.

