Hospitalisation for administrative reason (for observation or social reasons) is allowed at the investigator's discretion and will not qualify as serious unless there is an associated adverse event warranting hospitalisation (see [Appendix I](#) and [Appendix II](#) for additional safety information).

The causality of AE/SAEs (i.e., their relationship to trial treatment) will be assessed by the individual investigators at each trial centre who must while completing the CRF answer yes/ no to the question 'do you consider that there is a reasonable possibility that the AE/SAE may have been caused by the investigational drug?'

Any events that are unequivocally due to disease recurrence must not be reported as AEs.

The specialist group handling the pharmacovigilance for the study is:

[REDACTED]

The [REDACTED] is specialised and has the appropriate expertise in handling and reporting SAEs.

9.2.1.2. *Adverse Event Reporting*

For the purpose of this trial, any detrimental change in a patient's condition, subsequent to their entry into the trial and during the 28-day follow-up period after the final treatment, should be considered an AE.

The development of a new cancer should be regarded as an AE. New cancers are those that are not the primary reason for the administration of the trial treatment and have been identified after the patient's inclusion into this clinical trial.

Any events that are unequivocally due to disease recurrence must not be reported as AEs.

If the same AE occurs at several investigation times in one patient, then the AE in question must be documented and assessed as new each time.

All AEs are to be recorded on the CRFs provided and Serious Adverse Events also on the Serious Adverse Event Form. A description of the event, including its severity, duration, any action taken (e.g. treatment and follow-up tests) and the outcome is to be provided, along with the investigator's assessment of the relationship to the trial treatment. AEs and laboratory values will be graded according to the NCI Criteria for Adverse Events (CTCAE) (v4.03: June 14, 2010) and recorded on the appropriate CRF page.

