Additional information will be requested, if necessary, by the Trial Physician within 5 days of the receipt of the SAE report. This is to ensure that the initial reporting of SAEs is made to the regulatory authorities within the required time-frame. All withdrawals from trial treatment must be notified to the trial physician. Withdrawals from treatment due to a new, previously unreported SAE must be notified to the Trial Physician, along with the SAE. Withdrawal from trial treatment for a previously reported SAE can be made within the 7 days after the decision has been made to withdraw the patient and for a non-serious AE within 21 days of the decision to withdraw. After withdrawal from treatment patients must be followed up for AEs for 28 days after the last dose of trial medication. All SAEs recorded during that period must be reported to the safety group, and followed up until resolved unless in the Investigator's opinion the condition is unlikely to resolve due to the patient's underlying progressive disease.

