9.2.2. Safety Laboratory Variables

Safety serum chemistry and haematology parameters will be analysed at hospitals local laboratory.

Blood samples for the determination of serum chemistry and haematology will be drawn at pre-specified time-points, see Schedule of visits ([Table 6-1](#)) Additional haematology and chemistry are under the investigator's judgement.

The following laboratory tests will be performed:

Table 9-1: Clinical laboratory parameters

Chemistry	Haematology
Total Alkaline Phosphatase (total ALP)	RBC count
ALT (SGPT)	Hb
AST (SGOT)	Haematocrit
Lactate Dehydrogenase (LDH)	PLT count
Gamma-GT	WBC count
Total Protein	WBC diff.
Albumin	Neutrophils
Bilirubin	Lymphocytes
Creatinine	Monocytes
Sodium	Eosinophils

Chemistry	Haematology
Potassium	Basophils
Magnesium	
Calcium	
Phosphate	
Chloride	
Urea	
Oestradiol (females at screening only)	

Reference ranges from each laboratory will be provided to the Sponsor. If during the study, ranges should be changed, investigators are requested to provide updated laboratory normal values.

Laboratory values with CTCAE grade 3 or higher and/or considered clinically significant by the treating physician have to be reported as an AE during the treatment period. At the follow-up visit only changes in laboratory values judged to be related to the study drug will be reported.

Volume to be drawn from each patient

The total volume of blood that will be drawn from each patient in this trial will vary depending on how long the patient stays on study. [Table 9-2](#) indicates the range for patients completing the whole study period.

Table 9-2: Volume of blood to be drawn from each subject

Assessment		Sample volume (ml)	No. of samples	Total volume (ml)
PBMC		50 ml	2-3	100-150 ml
Biomarkers (CEA)/ other immune subsets		7 ml	2-3	14-21 ml
Safety	Clinical chemistry	7 ml	5-6	35-42 ml
	Haematology	7 ml	5-6	35-42 ml
CTCs		6 ml	2-3	12-18 ml
Total		67 ml		196-273 ml

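### End-of-study adverse-event recording leaves out pembrolizumab in Part II, and the protocol does not say which rule governs non-serious events that start after surgery

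*Protocol*

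**What the plan says.** - **Filter at the end-of-study visit.** Protocol section 6.4.3 lists "Adverse events and concomitant medications deemed to be related to TG02-treatment". In Table 6-1 (section 6.4.4) the adverse-event row carries the same limit in the end-of-study column: "a: Deemed to be related to TG02-treatment".
- **Meaning of the term.** Section 4.2: "This GM-CSF/TG02 combination is referred to as TG02-treatment in this study protocol". Table 6-1 footnote p: "TG02-treatment is a combination of the two IMPs: GM-CSF and TG02". For Part II, section 8.1 says that "in addition to TG02 and GM-CSF, a third IMP, pembrolizumab will be used".
- **General rule.** Under section 9.2.1.2, any detrimental change "subsequent to their entry into the trial and during the 28-day follow-up period after the final treatment, should be considered an AE". For patients withdrawn from treatment, the same section adds: "After withdrawal from treatment patients must be followed up for AEs for 28 days after the last dose of trial medication". Neither sentence has a causality condition.
- **Laboratory values.** Section 9.2.2: "At the follow-up visit only changes in laboratory values judged to be related to the study drug will be reported".
- **Visit timing.** Section 6.4.3 places the visit in the post-operative hospital stay, up to 6 weeks after surgery. The synopsis puts it about 4 weeks after surgery, and section 6.4.4 gives 4 weeks of follow-up. Section 6.4 says both about 6 weeks and within 6 weeks.
- **Analysis.** SAP section 5.2 assesses relationship to TG02, GM-CSF and pembrolizumab separately and plans a table of events related to pembrolizumab only. Its treatment-emergent definition has a start (first IMP) but no end and no relatedness condition.

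**The concern.** Adverse events are a primary endpoint, and the synopsis calls the Part II combination a novel treatment. Yet the one scheduled post-operative collection asks about two of the three IMPs. The pembrolizumab-only table in the SAP needs events that this visit does not request.

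The second problem is that the filter and the general rule differ in scope. A site working from the visit schedule and a site working from section 9.2.1.2 could record different non-serious events after surgery. The SAP would pool both kinds of record in one table without showing it, and would set Part I and Part II side by side. With up to 10 patients in Part II, one patient counted or not counted moves a percentage by 1/10, or 10 points.

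**Working it through.** The plan gives no figure on this point to reproduce. The check compares the texts and then runs a calendar on nominal days.

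**1. Does the filter apply to adverse events?** In section 6.4.3 alone, the relatedness phrase could attach only to concomitant medications. Footnote a sits on the adverse-event row of Table 6-1, which removes that reading.

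**2. Does the filter include pembrolizumab?** No. Section 4.2 and footnote p define the term as GM-CSF plus TG02. The adverse-event definition in section 9.2.1.1 has the same omission, since it names only GM-CSF/TG02 as the investigational product.

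**3. Which rule covers which days?** Adverse events are monitored continuously in the treatment period, which runs to surgery (section 6.4.2). Table 6-1 then goes to the filtered end-of-study entry. It does not say which rule covers the days in between.

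**4. How far does the 28-day period run past surgery?** Let S be the surgery day.

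Days past surgery = max(0, last dose day + 28 − S)

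Inputs are from section 6.4.2 and Table 6-1:
- Last vaccination: Day 36 if S ≤ 64, otherwise Day 64.
- Last pembrolizumab dose: Day 36 if S = 50; Day 50 if S = 51 to 64; Day 64 if S ≥ 65.
- Last TG02 injection given only as a DTH test: Day 48 if S = 50; Day 50 if S = 51 to 64. For S ≥ 65 in DTH-negative patients it is Day 64 (section 6.4.2) or S − 2 (footnote i).

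| Final treatment taken as | S = 50 | S = 51 | S = 64 | S = 65 | S = 92 |
|---|---|---|---|---|---|
| Last vaccination (Part I) | 36+28−50 = 14 | 36+28−51 = 13 | 36+28−64 = 0 | 64+28−65 = 27 | 64+28−92 = 0 |
| Last pembrolizumab dose (Part II) | 36+28−50 = 14 | 50+28−51 = 27 | 50+28−64 = 14 | 64+28−65 = 27 | 64+28−92 = 0 |
| DTH-only injection counted as a dose (both parts) | 48+28−50 = 26 | 50+28−51 = 27 | 50+28−64 = 14 | 64+28−65 = 27 (Day 64 test) | 0 (Day 64 test) or 90+28−92 = 26 (footnote i) |

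The range is 0 to 27 days. Table 6-1 allows 4 days either side for week 8. Surgery on Day 46 after a Day 36 dose gives 36+28−46 = 18, inside the range.

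The Day 64 column depends on texts that disagree:
- **Vaccination.** Footnote f gives none at week 10 when surgery is in week 10, and the table follows it. Note 3 to Figures 2 and 3 gives one unless surgery came before week 10. That would make the result 64+28−64 = 28.
- **Pembrolizumab.** The synopsis and Table 8-1 tie the week-8 infusion to surgery on Days 51 to 63. On that wording the result is 36+28−64 = 0 instead of 14.

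**5. When do the rules clash?** Suppose the visit is v days after surgery. The part of the 28-day period still open at the visit is at most 27 − v days. For v = 28 this is −1, so the period has always ended. For v = 14 (an assumption, since the hospital stay has no stated length) it is up to 13 days; for v = 7 (also an assumption), up to 20. Section 6.2 ends study participation at that visit.

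**6. What is left to the filter alone if the rules run in sequence?** In Part II, counting from the last pembrolizumab dose, this is v minus the step-4 result. A visit at 28 days leaves 28−27 = 1 to 28−0 = 28 days. A visit at 42 days leaves 42−27 = 15 to 42−0 = 42 days. In that stretch the visit does not ask for a new non-serious event attributed only to pembrolizumab.

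**The case against.** A reader might infer that the filter flatly contradicts the 28-day rule. The documents do not support that. Section 6.4.3 describes one visit, while section 9.2.1.2 sets the reporting period, and section 9.2.1 tells all staff to know its content. With a visit about 4 weeks after surgery, as in the synopsis, the rules fit in sequence: all causes first, related events only afterwards. A clash needs an early visit or a filter that reaches back to surgery. This part of the objection stands.

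A reader might also infer that pembrolizumab toxicity after surgery goes uncollected. That too is wrong. All SAEs are reported whatever the cause (section 9.2.1.2). Known treatment-related toxicities are followed to resolution (section 6.4). Under section 9.2.3, clinically significant worsening on physical examination is an adverse event whatever its cause, and the end-of-study visit includes an examination. The gap is confined to new non-serious events not found on examination.

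The study-drug wording in section 9.2.2 need not be a narrower scope, since section 8.4 uses the plural just after covering storage of all three products. It is unclear rather than wrong.

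A relatedness filter may be a reasonable way to keep routine surgical complications out of the data. That would justify limiting collection to related events. It would not justify leaving out one of the IMPs.

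**Conclusion.** The omission of pembrolizumab is wrong as written and follows from the protocol's own definitions. It does not depend on any day count.

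The relation between the two rules is unresolved rather than certainly contradictory. The 28-day period runs 0 to 27 days past surgery. How much of it is exposed to the filter depends on when the visit is held and whether the filter looks back to surgery. The range assumes nominal days without dosing-visit windows and follows footnote f for Day 64 surgery. Final treatment is not tied to a named IMP, and the protocol does not say whether DTH-only injections count. The day counts are not proportions of patients, because the documents give no distribution of surgery dates.

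Section 4.2 reports four patients treated with TG02, the fourth having completed the trial. Part I dosing therefore appears largely complete, and a change would mainly affect the up to 10 patients of Part II. The point should be corrected: the affected events are non-serious, but they belong to a primary endpoint and the correction is cheap.

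**What to change.** 1. In section 6.4.3 and Table 6-1 footnote a, make the filter refer to events related to any IMP (TG02, GM-CSF or pembrolizumab). Align sections 9.2.1.1 and 9.2.2 with that wording.
2. In section 9.2.1.2, state that the all-cause rule governs until 28 days after the last dose of any IMP, including after surgery and when the end-of-study visit comes earlier. State that the IMP-related filter applies only after that, and whether DTH-only TG02 injections count as doses.
3. In SAP section 5.2, state where collection changes from all-cause to IMP-related.
4. Reconcile the end-of-study visit timings in the synopsis and sections 6.4, 6.4.3 and 6.4.4. The conflicting Day 64 dosing texts and the two timings of the extra DTH test also need reconciling. No dose, DTH timing or clinical rule is proposed here.

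The cost is wording in a few protocol sections, one SAP sentence, and a few more non-serious post-operative entries. Patients whose visit falls before the 28 days end would need some means of collecting events up to that day.
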